5.3.1 Adverse Events

The applicable definition of an AE is in the study protocol. All AEs occurring from when a subject signs informed consent to when a subject exits the study will be accounted for in the reporting.

Analysis and presentation of AEs will be separated into pre-treatment AEs, between-treatment AEs and treatment-emergent AEs as defined below:

- Pre-treatment: an event that occurs after signing informed consent but prior to exposure to study lenses.
- Between-treatment: an event that occurs one day after last exposure to Period 1 lenses but prior to exposure of Period 2 lenses.
- Treatment-emergent: an event that occurs from exposure to Period 1 study lenses until the subject exits from the study, excluding those classified as between-treatment.

The following tables and supportive listings will be provided:

- Incidence of All Ocular Treatment-Emergent Adverse Events
- Incidence of Ocular Serious Treatment-Emergent Adverse Events
- Incidence of All Nonocular Treatment-Emergent Adverse Events
- Incidence of Nonocular Serious Treatment-Emergent Adverse Events
- Listing of All Ocular Treatment-Emergent Adverse Events
- Listing of All Nonocular Treatment-Emergent Adverse Events

- Listing of All Ocular Pre-Treatment Adverse Events
- Listing of All Nonocular Pre-Treatment Adverse Events
- Listing of All Ocular Between-Treatment Adverse Events
- Listing of All Nonocular Between-Treatment Adverse Events

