## **10.3 Unscheduled Visits**

If a subject visit occurs between any regularly scheduled visit and the visit is conducted by study personnel, this visit must be documented as an Unscheduled Visit. If the subject seeks medical attention outside the clinic (for example, at an Emergency Room) or at the clinic but is seen by nonstudy personnel, the investigator is to capture adverse event-related information on the Adverse Event form upon becoming aware.

During all unscheduled visits, the investigator must conduct the following procedures:

- Collect Adverse Event information
- Record changes in medical condition or concomitant medication
- Collect device deficiency information
- Biomicroscopy

The investigator may perform additional procedures for proper diagnosis and treatment of the subject according to Table 3-1 or at their discretion. The investigator must document this information in the subject's case history source documents.

If during an Unscheduled Visit the subject is discontinuing the IP or discontinuing from the study, the investigator must conduct Exit procedures according to Table 3-1 Schedule of Study Procedures and Assessments, as possible.

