## **12.6 Safety Analyses**

The safety endpoints are:

- AEs
- Biomicroscopy findings
- Device Deficiencies

There are no safety hypotheses planned in this study. The focus of the safety analysis will be a comprehensive descriptive assessment of occurrence of adverse events as well as the other listed parameters.

All AEs occurring from the time a subject signs informed consent to study exit will be accounted for in the reporting. Safety analyses will be conducted using the safety analysis set on a treatment-emergent basis. Descriptive summaries (frequencies and percentages) for ocular and nonocular AEs will be presented by Medical Dictionary for Regulatory Activities Preferred Terms. AEs leading to study discontinuation and SAEs will be identified. Individual subject listings will be provided, as necessary.

Individual subject listings will be provided for AEs that occur after signing informed consent but prior to exposure to IP, as well as for AEs that occur between treatment periods.

Each biomicroscopy parameter will be tabulated by its grade. For each biomicroscopy parameter, counts and percentages of eyes that experience an increase of  $\geq 2$  grades from baseline (last assessment prior to study lens exposure) to any subsequent visit within the same period will be presented. A supportive listing will be generated which will include all biomicroscopy data from all visits within the same period for those eyes experiencing the increase.

[figure not shown]
Two listings for device deficiencies, prior to exposure to study contact lenses and treatment-emergent, will be provided. Additionally, each device deficiency category will be tabulated.

No inferential testing will be conducted for the safety analyses.

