2 ANALYSIS SETS

2.1 Safety Analysis Set

Safety analyses will be conducted using the safety analysis set on a treatment-emergent basis. As such, the safety analysis set will include all subjects/eyes exposed to any study lenses evaluated in this study.

For treatment-emergent safety analyses, subjects/eyes will be categorized under the actual study lenses exposed in the corresponding lens sequence.

Adverse events occurring from the time of informed consent but prior to first exposure to study lenses will be summarized in subject listings.

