5.3 Statistical Methods for Safety Analyses

The analysis set for all safety analyses is defined in Section 2.1. Baseline will be defined as the last measurement prior to exposure to study lenses. For biomicroscopy data, baseline will be defined as Visit 1 for Period 1 and Visit 2 for Period 2. Safety variables will be summarized descriptively.

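### Are adverse events that begin in the gap between the two lenses wrongly kept out of the incidence tables?

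*SAP*

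**What the plan says.** SAP 5.3.1 divides adverse events into three classes: pre-treatment, between-treatment and treatment-emergent. The middle class is worded "Between-treatment: an event that occurs one day after last exposure to Period 1 lenses but prior to exposure of Period 2 lenses". The treatment-emergent class is "an event that occurs from exposure to Period 1 study lenses until the subject exits from the study, excluding those classified as between-treatment". Four incidence tables follow, for all and for serious events, ocular and nonocular; one of them is "Incidence of Ocular Serious Treatment-Emergent Adverse Events". All four are restricted to treatment-emergent events. Pre-treatment and between-treatment events each get an ocular and a nonocular listing.

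Protocol 12.6 places safety analysis on a treatment-emergent basis. It calls for individual listings of events before exposure to the product, "as well as for AEs that occur between treatment periods".

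Three other rules bear on the point:

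- **Attribution to a lens.** In SAP 2.1, "subjects/eyes will be categorized under the actual study lenses exposed in the corresponding lens sequence". The sentence opens by limiting itself to treatment-emergent safety analyses.
- **Biomicroscopy.** SAP 5.3 says "For biomicroscopy data, baseline will be defined as Visit 1 for Period 1 and Visit 2 for Period 2". Protocol 12.6 counts a rise of two or more grades from that baseline "to any subsequent visit within the same period will be presented".
- **Stopping a lens.** Protocol 10.3 says "If during an Unscheduled Visit the subject is discontinuing the IP or discontinuing from the study, the investigator must conduct Exit procedures". Protocol 10.4.2 seeks to keep a subject who stops treatment under assessment until the final visit.

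**The concern.** Read literally, the definitions treat the two periods differently. An event three days after the first lens is stopped, with the second not yet worn, is only listed. An event three days after the second lens is stopped, before exit, is counted. The exclusion can only lower tabulated incidence, and only in Period 1.

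It also seems at odds with the biomicroscopy rule, under which a sign found at Visit 2 counts in Period 1 however early the lens was stopped. An adverse event for the same sign, with onset in the gap, would not be counted.

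Since safety is purely descriptive, the incidence tables are its main summary. If lenses are stopped early because of a lens problem, the missing events could be the ones a reader most wants to see.

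**Working it through.** **1. Do the documents agree?** Protocol 12.6 puts events between periods in the same sentence, and in the same kind of output, as events before exposure. The SAP gives each its own class and listings, and tabulates the rest. All events from consent to exit are accounted for (SAP 5.3.1), and Protocol 12.6 has serious events and those leading to discontinuation identified. No passage is contradicted and no event is lost.

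**2. Timing inputs.**
- Visit 2 is 8 to 11 days after Visit 1, and Visit 3 is 8 to 11 days after Visit 2 (Protocol 10).
- Check against the plan's own figures: 8 + 8 = 16 and 11 + 11 = 22, matching the stated 16 days of exposure and the maximum of 22 days of participation.
- The first lens is worn for at least 16 hours on the day before Visit 2 (Protocol 7.1), and acuity is measured with study lenses at Visit 2 (Protocol Table 3-1).
- At least 12 hours without lenses follow Visit 2 (Protocol 7.1).
- Assumed: the second lens is first worn the day after Visit 2.

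**3. On schedule.** Let Visit 1 be day 0, V2 the day of Visit 2, and k the last day of first-lens wear. The window opens on day k + 1 and closes when the second lens goes in on day V2 + 1:

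excluded days = (V2 + 1) − (k + 1) = V2 − k.

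With k = V2 this is 0. If one day means 24 hours and the second lens starts h hours after the first was last worn, the window is max(0, h − 24) hours: 0 at h = 12 or 24, 12 at h = 36, and 24 at h = 48. If one day means the next calendar day, only the hours from midnight to insertion remain, about 7 with an assumed 07:00 insertion.

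**4. Off schedule (assumed departures).**

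| Last first-lens wear, day k | Excluded days, V2 = 8 to 11 |
|---|---|
| 1 | 7–10 |
| 3 | 5–8 |
| 5 | 3–6 |
| 7 | 1–4 |

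If the first lens is worn to Visit 2 and the second starts d days later, d − 1 days are excluded: 1, 2 or 3 days for d = 2, 3 or 4.

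**5. The same stop in Period 2.** Counting the exit-visit day as Visit 2 was counted above, the days after last wear number V − k, where V is 8 to 11. That gives 7–10 days for k = 1 and 0 on schedule. Leaving out the exit day gives V − (k + 1), which is −1 on schedule; any one-day difference between the periods comes from that convention. The two tails are equally long. Only their classification differs, and on schedule both are empty.

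**6. Who could fall in the window?** A temporary pause does not open it, because the last exposure is then the later wear. The long windows need a subject who gives up the first lens for good and afterwards wears the second. No visible text describes that route: Protocol 10.3 points to exit procedures, and 10.4.2 speaks of continued assessments, not of moving to the second lens. A problem that led to stopping began on or before the last wear, so it is treatment-emergent and tabulated. A further one-day margin follows. What remains is a new event that starts later, while no study lens is worn.

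**7. The rules said to conflict.** SAP 2.1 attributes events that are already treatment-emergent; it does not assign lens-free events to the first lens. Biomicroscopy is graded at visits against a period baseline, whereas adverse events are classified by onset. Different data call for different rules, and the biomicroscopy rule in fact softens the effect: a rise of two or more grades found at Visit 2 is tabulated under Period 1 in any case.

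**8. Size.** One omitted subject is 1/116 = 0.86 percentage points, taking the 116 planned completers as the assumed denominator per lens. With 1:1 allocation to sequence, each lens is the Period 1 lens in about half the subjects. The comparison of lenses is affected only if early stops or late starts differ by lens, and the documents give no rates.

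**The case for a change.** The strongest reply is that Protocol 12.6 asks for a listing but neither defines the interval between periods nor says in terms that its events leave the tables. Starting the window at last exposure, possibly days before Visit 2, is the SAP's choice. Stopping for symptoms is foreseeable, since Protocol 5.3 tells subjects to remove lenses and return promptly. The 12 hours is a minimum with no visible maximum. Counting gap events under the first lens, with a flag, would need no new data.

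Part of this stands. The period asymmetry is real on the literal wording. The SAP does not say whether one day is 24 hours or the next calendar day. For a subject who never wears the second lens, the text can be read as counting later events to exit or as excluding them. These are missing details that programming rules can settle.

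The rest does not make a defect. Pairing gap events with pre-exposure events, under an analysis declared to be treatment-emergent, is good evidence that the separation is intended. Counting lens-free events under the first lens is another defensible convention, but it would add unrelated off-lens events to that lens and blur a separation the protocol makes. Some text on exposure, and the lead-in to the 12-hour requirement, is blacked out, so a stricter claim about gap timing cannot be tested.

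**Conclusion.** The concern does not hold. Setting between-period events apart is a deliberate classification, consistent between protocol and SAP, in a descriptive safety analysis that still reports every event. On schedule it removes 0 whole days, assuming the second lens is first worn the day after Visit 2. Off schedule it can remove from 1 day up to about 10 under the stop dates and one-to-three-day delays assumed above. That applies only to new events starting while no study lens is worn, in subjects who stop the first lens for good and later wear the second, or who start the second late. The number of such subjects cannot be derived from the documents, and no bias between the lenses is shown. Whether to tabulate such events under the first lens is a choice on which statisticians may reasonably differ.

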5.3.2 Biomicroscopy Findings/Slit Lamp Examination

The following tables and supportive listings will be provided:

- Frequency and Percentage for Biomicroscopy Findings by Visit
- Incidence of Increased Severity by 2 or More Grades in Biomicroscopy Findings
- Listing of Subjects With Other Biomicroscopy Findings
- Listing of Subjects With Conjunctival Compression/Indentation or Chemosis
- Listing of Subjects With Increased Severity by 2 or More Grades in Biomicroscopy Findings [This listing will include all relevant visits within the crossover period]
- Listing of Subjects with Infiltrates

5.3.3 Device Deficiencies

The following tables and supportive listings will be provided:

- Frequency of Treatment-Emergent Device Deficiencies
- Listing of Treatment-Emergent Device Deficiencies
- Listing of Device Deficiencies Prior To Treatment Exposure

7 SAMPLE SIZE AND POWER CALCULATIONS

Sample size calculation is based on a prior clinical study [REDACTED] which evaluated performance of PRECISION1 and Biotrue. [REDACTED]

Primary Effectiveness

[figure not shown]
[figure not shown]
To demonstrate noninferiority (margin = 0.05 in logMAR; $\frac{1}{2}$ line in Snellen) in distance VA as a one-tailed hypothesis with $\alpha=0.05$, and using a standard deviation of 0.0462 for paired differences, 80% power can be attained with a sample size of 8 (4 per sequence).

[figure not shown]
10 APPENDIX

Table 10-1 Overview of Study Plan

Procedure / Assessment	Prescreening (optional)	Visit 1 Screening / Baseline / Dispense Lens 1 [REDACTED]	Visit 2 Week 1 Follow-up Lens 1 / Dispense Lens 2 [REDACTED]	Visit 3 Week 1 Follow-up Lens 2 / Exit [REDACTED]	Early Exit	Unscheduled Visit
		[REDACTED]	8 (-0/+3) days after Visit 1 [REDACTED]	8 (-0/+3) days after Visit 2 [REDACTED]	N/A	N/A
Informed Consent		✓				
Demographics		✓				
Medical History [†]		✓	✓	✓	✓	✓
Concomitant Medications [†]		✓	✓	✓	✓	✓
Inclusion/Exclusion		✓				
Habitual lens information (brand, power, lens solution)		✓				
VA with habitual correction (OD, OS, logMAR distance) *		✓		✓ (Exit procedure)	✓	(✓)
Manifest refraction (OD, OS, logMAR distance) *		✓	(✓)	(✓)	(✓)	(✓)
BCVA with manifest refraction (OD, OS, logMAR distance)		✓	(✓)	(✓)	(✓)	(✓)
Biomicroscopy		✓	✓	✓	✓	✓
[REDACTED]	[REDACTED]	[REDACTED]				

Procedure / Assessment	Prescreening (optional)	Visit 1 Screening / Baseline / Dispense Lens 1	Visit 2 Week 1 Follow-up Lens 1 / Dispense Lens 2	Visit 3 Week 1 Follow-up Lens 2 / Exit	Early Exit	Unscheduled Visit
		[REDACTED]	[REDACTED]	[REDACTED]	N/A	N/A
Trial lens fitting (Test and Comparator) & assessments: *						

 • VA (logMAR distance) • [REDACTED] • [REDACTED] • [REDACTED] 		✓				
Randomize ♦		✓				
Dispense (provide) study lenses *		✓	✓			(✓)
VA (logMAR distance) with study lenses, (OD, OS)			✓	✓	(✓)	(✓)
[REDACTED]			■	■	■	■

Procedure / Assessment	Prescreening (optional)	Visit 1 Screening / Baseline / Dispense Lens 1	Visit 2 Week 1 Follow-up Lens 1 / Dispense Lens 2	Visit 3 Week 1 Follow-up Lens 2 / Exit	Early Exit	Unscheduled Visit
						
					N/A	N/A
AEs		✓	✓	✓	✓	✓
Device Deficiencies ~		✓	✓	✓	✓	✓

Procedure / Assessment	Prescreening (optional)	Visit 1 Screening / Baseline / Dispense Lens 1	Visit 2 Week 1 Follow-up Lens 1 / Dispense Lens 2	Visit 3 Week 1 Follow-up Lens 2 / Exit	Early Exit	Unscheduled Visit
						
Exit Form		(✓)	(✓)	✓	✓	(✓)

(✓) Assessment performed as necessary, e.g., decrease of VA by 2 lines or more with investigational product (IP) compared to BCVA with manifest refraction at Visit 1

◊ Randomization should occur at Visit 1 unless communicated otherwise by the sponsor.

‡ All ocular and targeted systemic meds / medical history
